After screening, PCV13 naïve subjects will be randomized within each cohort to receive ASP3772 or PCV13. Subjects randomized to ASP3772 will receive a single dose of ASP3772 administered as a 0.5 mL intramuscular injection into the deltoid muscle of the right or left arm on day 1, at 1 of 3 dose levels: 1, 2 or 5 µg of ASP3772 for Cohorts 4, 5 and 6, respectively. The subjects randomized to PCV13 will receive a single injection of the standard dose of PCV13.

Approximately 396 subjects will be enrolled in Stage 2 of the study; 132 subjects per cohort (ASP3772 n = 99 and PCV13 n = 33).

Stage 2 will commence after the DEC has evaluated safety (including reactogenicity) data through 30 days from all cohorts in Stage 1. Dose escalation to Cohort 5 (intermediate dose, 2 μ g) in Stage 2 will commence once the DEC has evaluated Stage 2 Cohort 4 (1 μ g) safety (including reactogenicity) and tolerability through 7 days postimmunization. Dose escalation into Cohort 6 (high dose, 5 μ g) in Stage 2 will commence once the DEC has evaluated Stage 2 Cohort 5. Randomization for Stage 2 subjects will be stratified by age (65 to 74 years of age and 75 to 85 years of age) to ensure there is a balanced number of subjects immunized with PCV13 and ASP3772 with immunogenicity data across the elderly population.

Safety and tolerability assessments including adverse events (AEs) will continue through 30 days postimmunization. Safety assessments for SAEs and MAAEs including PIMMCs and NOCDs will continue through day 180 postimmunization.

Data will be collected in an observer-blinded manner (vaccine recipients and those responsible for evaluation of any study endpoint will be unaware of which vaccine the subject received).

Serum samples to measure IgG and OPA will be collected prior to study immunization on day 1 and postimmunization on day 30.

Primary immunogenicity evaluation for dose finding is 30 days following the initial immunization.

Stage 2 Group 3:

A separate group of elderly subjects previously immunized with PCV13 will be enrolled and receive the recommended booster immunization with PPSV23 only (n = 99) (Group 3).

Study Design Overview (continued):

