All statistical comparisons will be made using two sided tests at the $\alpha=0.05$ significance level unless specifically stated otherwise and 95% confidence intervals will be provided. All null hypotheses will be of no treatment difference; all alternative hypotheses will be two-sided, unless specifically stated otherwise.

All data processing, summarization, and analyses will be performed using SAS®Version 9.1.3 or higher on Unix. Specifications for table, figures, and data listing formats can be found in the TLF specifications for this study.

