To obtain the GMFR, calculate the fold rise for each subject. Take the natural log using LOG function in SAS. Using PROC FREQ on the log transformed values obtain the mean and standard deviation of the log transformed values. Exponentiate mean and standard deviation to obtain the geometric mean and geometric standard deviation.

To obtain the lower confidence limit of the 95% confidence interval of the GMFR obtain the critical value of the student's distribution using TINV (0.975, n-1) where n=the number of subjects. For example, with 20 subjects TINV (0.975, 19) = 2.093. The lower 95% confidence interval is then:

$$GM / GSD^{(TINV(0.975, n-1) / SQRT(n))}$$

and the upper 95% confidence is calculated using: $GM \times GSD^{(TINV(0.975, n-1) / SQRT(n))}$

where SQRT is the square root.

Comparing the Geometric Mean Fold Rise (GMFR) between two groups

To compare the GMFR between the two treatment groups (each dose of ASP3772 vs. PCV13) use an analysis of covariance with the log-transformed post immunization value as the dependent variable and the log-transformed pre vaccination value as the independent value. With log-transformed antibody values (titer or IgG levels) the variability usually decreases with increasing antibody values (heteroscedasticity).

Assume heteroscedasticity exists and use the following model to analyze the data.

```
proc mixed;  
  model y=group x group*x/ solution; repeated / local=exp ( x x2);  
  run;
```

Where: y= log-transformed post immunization antibody titer (or IgG concentration)

x= log-transformed pre immunization antibody titer (or IgG concentration)

x2=(log-transformed pre immunization antibody titer (or IgG concentration))² group= treatment group

group*x= treatment group by pre immunization log-transformed antibody titer (or IgG concentration). If group*x is significant then there is heteroscedasticity.

Use the ESTIMATE and CL options in proc mixed to obtain the estimate of the baseline corrected mean fold ratio and the 95% confidence interval for the baseline corrected mean fold ratio. The ratio is the GMFI for ASP3772 / PCV13. The baseline-corrected geometric mean ratio of the two treatment groups is:

2^{β_1} where β_1 is the estimate of the treatment group effect obtained from the ANCOVA. The 95% lower confidence limit is then $2^{\beta(LCL)}$ and the 95% upper confidence interval is then $2^{\beta(UCL)}$ LCL and UCL are the 95% confidence limits obtained from the CL option in Proc Mixed.

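### SAP Appendix A reads a significant treatment-by-baseline term as heteroscedasticity, when it tests whether the ASP3772/PCV13 ratio depends on baseline antibody

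*SAP*

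**What the plan says.** SAP Section 10.1 (Appendix A), under the comparison of GMFR between two groups, compares each ASP3772 dose with PCV13 by an analysis of covariance on log antibody.

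- It says what it means by heteroscedasticity: "With log-transformed antibody values (titer or IgG levels) the variability usually decreases with increasing antibody values (heteroscedasticity").
- It takes it as given: "Assume heteroscedasticity exists and use the following model to analyze the data".
- The code is PROC MIXED with "model y=group x group*x/ solution; repeated / local=exp ( x x2").
- It defines the product term: "group*x= treatment group by pre immunization log-transformed antibody titer (or IgG concentration").
- It then gives its only reading of that term: "If group*x is significant then there is heteroscedasticity".
- The reported ratio is a back-transformed β1, which "is the estimate of the treatment group effect obtained from the ANCOVA". Confidence limits are back-transformed in the same way.

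The appendix does not say that `x` is centred, at which baseline the ratio is evaluated, or what to report if slopes differ. SAP Section 7.1 sets the general testing rule ("All statistical comparisons will be made using two sided tests at the" 0.05 level).

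**The concern.** In the SAP's code, `group*x` stands in the MODEL statement. Its coefficient is the difference between vaccines in the slope of log post-immunization on log pre-immunization antibody. A significant result says that the ASP3772/PCV13 ratio is not the same at every baseline level. It says nothing about residual spread, which the REPEATED statement models through `x` and `x2`.

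The analyst is therefore told to read effect modification by baseline as a variance matter that the model already covers, and then to quote one ratio. With `group*x` in the model and `x` uncentred, the group coefficient is the log ratio at `x = 0`, that is, at a baseline titer or concentration of 1 in assay units. A significant interaction is the signal that a ratio at one arbitrary baseline is not enough, and the plan gives that signal a different meaning. If the vaccines differed mainly in people with low baseline antibody, nothing in the plan would lead the report to say so.

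**Working it through.** The documents give no power or error figure for this check, so there is none to reproduce. The sentence can be judged from the model, and its behaviour illustrated by simulation.

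**1. What the terms mean.** For group g (1 = ASP3772, 0 = PCV13):

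- Mean: E(y) = a + β1·g + b·x + d·g·x
- Variance: Var(y) = exp(γ0 + γ1·x + γ2·x²)
- Log ratio at baseline x: β1 + d·x

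Testing `group*x` tests d = 0. Heteroscedasticity in the SAP's sense is γ1 or γ2 ≠ 0. Either can be present without the other. β1 alone is the log ratio only at x = 0.

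**2. Simulation inputs.**

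- From the documents: the protocol design section gives "132 subjects per cohort (ASP3772 n = 99 and PCV13 n = 33"), and SAP Section 6.1.2 pools PCV13 over Cohorts 4 to 6, so each Stage 2 comparison is 99 v 3 × 33 = 99. Stage 1 is 30 v 3 × 10 = 30. Tests are two-sided at 0.05.
- Assumed, not in the documents: x with mean 0 and SD 1 (natural log), residual SD 1 at x = 0, common slope 0.5, log effect 0.3 at x = 0, slope gap 0, 0.3 or 0.5, and log-variance slope 0, −0.5 or −1.
- The SAP model was fitted by REML, with 1,500 trials per scenario and n − 4 degrees of freedom for the test of `group*x`.

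**3. Share of trials in which `group*x` is significant.**

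| Scenario | 99 v 99 | 30 v 30 |
|---|---|---|
| No slope gap, constant variance | 7.1% | 9.5% |
| Slope gap 0.3, constant variance | 55.5% | 25.4% |
| Slope gap 0.5, constant variance | 93.4% | 51.1% |
| Parallel slopes, log-variance slope −0.5 | 6.3% | 9.1% |
| Parallel slopes, log-variance slope −1 | 5.5% | 7.8% |

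The check responds to unequal slopes. Under real heteroscedasticity it fires no more often than when neither feature is present. A likelihood-ratio test of γ1 and γ2 in the same Stage 2 trials flagged heteroscedasticity in 99% to 100% when present and in 5% when absent.

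**4. Sensitivity to the residual SD.** With constant variance, SE(d) ≈ SD × √(2/99), and power ≈ P(Z > 1.96 − 0.3/SE) for a gap of 0.3:

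- SD 1: SE = 0.142, 0.3/SE = 2.11, power about 56%
- SD 1.5: SE = 0.213, 0.3/SE = 1.41, power about 29%
- SD 2: SE = 0.284, 0.3/SE = 1.06, power about 18%

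**5. What one ratio can hide.** With log effect 0.3 at x = 0:

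| Slope gap | Ratio at −1 SD | At mean | At +1 SD |
|---|---|---|---|
| 0.3 | exp(0.0) = 1.00 | exp(0.3) = 1.35 | exp(0.6) = 1.82 |
| 0.5 | exp(−0.2) = 0.82 | exp(0.3) = 1.35 | exp(0.8) = 2.23 |

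These use natural logs. The appendix back-transforms β1 with base 2, which is a separate matter.

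**6. Number of tests.** 13 common serotypes × 3 doses × 2 assays = 78 per stage. Chance positives are 78 × 0.05 = 3.9 at the nominal level and 78 × 0.071 = 5.5 at the simulated Stage 2 null rate. At the simulated Stage 1 null rate the figure is 78 × 0.095 = 7.4.

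**The case against.** The strongest reply is that no choice of model depends on the sentence. The appendix assumes heteroscedasticity and fits the variance model in every case, so the check switches no model, estimate or interval. This stands. A reader might infer that real heteroscedasticity would slip through and damage the results, but the documents do not support that: the variance model does not wait to be triggered.

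Three further points carry weight.

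- **The single ratio comes from a different instruction.** Reporting β1 alone is required whether or not the sentence is there, so deleting the sentence cures only half the problem. That is why the fix also names the baseline at which the ratio is given. An ESTIMATE statement could be written at any baseline, but the SAP does not say which.
- **The scope is narrow.** SAP Section 7.4.1 lists GMFR relative to baseline within groups, and GMT and GMC ratios between groups. It does not list a between-group GMFR ratio in the visible text (part of 7.4.1, and all of 7.4.3, is redacted). For serotypes unique to ASP3772, Section 7.1 makes the comparison post-dose against pre-dose, so the point matters mainly for the 13 common serotypes. SAP Section 6 makes all immunogenicity endpoints secondary. Section 4 says Stage 2 responses will inform the phase 3 dose and sample size, but does not tie that to this comparison.
- **The slope gaps are assumed.** Nothing in the documents shows that baseline modifies the vaccine ratio, and the percentages move a good deal with the residual SD and the stage.

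None of this makes the sentence true. It remains the only interpretation of a significant interaction that the SAP offers.

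**Conclusion.** The statement is wrong as written and should be corrected. The consequence is that evidence of a baseline-dependent vaccine ratio would be read as a variance matter, while the reported ratio holds only at `x = 0`. That such a result would actually be labelled heteroscedasticity in the report is an inference, because the SAP specifies no output for the check.

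At 99 v 99, with the assumed ln baseline SD of 1 and residual SD of 1, a slope gap of 0.3 sets off the rule in about 56% of trials that have constant variance. The figure is about 29% at residual SD 1.5, and about 25% at 30 v 30 with SD 1. True heteroscedasticity with parallel slopes sets it off at about the null rate. The percentages rest on those assumptions; what the term tests does not. The affected analysis is a secondary immunogenicity comparison, and the primary safety endpoints are untouched.

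**What to change.** In SAP Appendix A:

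1. Delete the sentence that links `group*x` to heteroscedasticity. State instead that `group*x` assesses whether the ASP3772/PCV13 ratio depends on baseline antibody.
2. Report the ratio with its 95% CI at the median baseline for that serotype and assay, by an ESTIMATE statement for β1 + d × (median x) or by centring `x` at its median. Where the interaction is notable, add the ratios at the 25th and 75th percentiles.
3. Label the interaction tests exploratory and unadjusted. With 78 per stage, about 4 to 6 chance positives are to be expected, and perhaps 7 at Stage 1 size.
4. A test of the two variance parameters is optional, since that variance model is fitted regardless.

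The cost is a wording change, extra ESTIMATE statements and more table rows: at most 3 × 78 = 234 ratios per stage if every comparison were shown at all three percentiles, and more if the comparison is repeated in the Stage 2 age subgroups. No new data and no change to the fitted model are needed.

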For each local and systemic solicited reaction the percentage of subjects who reported each symptom by grade (None, Grade 1, 2, 3 or 4) will be summarized (n, %) by immunization group (PCV13 vs ASP3772) and dose level (ASP3772: 1, 2, 5 μ g) and the percentage of subjects who reported any symptom.

02 Dec 2019 Astellas Page 24 of 111

Analysis of Immunogenicity

Stage 1:

The following measures in adults 18 to 64 years of age will be used to characterize the immunological response 30 days following administration of either ASP3772 or PCV13. The following measures will be provided for each immunization group (PCV13 vs ASP3772) and dose level (ASP3772: 1, 2, 5 µg).

- The GMT, GSD and 95% confidence interval (CI) for functional OPA for each serotype will be calculated.
- The ratio of the OPA GMT (each ASP3772 dose level/PCV13) and 95% CI will be provided.
- The geometric mean concentration (GMC), GSD and 95% CI for serotype-specific IgG for each of the serotypes will be calculated.
- The ratio of the IgG GMC (each ASP3772 dose level/PCV13) and 95% CI will be provided.
- The GMFR, GSD and 95% CI will be calculated for each of the serotypes unique to ASP3772.
- The proportion of subjects with a ≥ 4-fold increase in anticapsular PS IgG and OPA relative to baseline will be calculated.

Stage 2; Group 2:

- The GMT, GSD and 95% CI for functional OPA activity for each serotype will be calculated.
- The ratio of the GMT for functional OPA (each ASP3772 dose level/PCV13) for each serotype and the 95% CI will be provided.
- The GMC, GSD and 95% CI for serotype-specific IgG for each of the serotypes will be calculated.
- The ratio of the GMC (each ASP3772 dose level/PCV13) and 95% CI will be provided for each serotype.
- The GMFR, GSD and 95% CI will be calculated for each of the serotypes unique to ASP3772.
- The proportion of subjects with $a \ge 4$ -fold increase in anticapsular PS IgG and OPA relative to baseline will be calculated.
- To assess the impact of ASP3772 dose, an analysis of covariance (ANCOVA) model with age (65 74, 75 85) as the covariate and immunization (ASP3772 1, 2, 5 μg or PCV13) as the factor of interest will be conducted on the natural logarithm (log) of pneumococcal OPA titers.
- To assess the impact of ASP3772 dose, an ANCOVA model with age (65 74, 75 85) as the covariate and immunization (ASP3772 1, 2, 5 μg or PCV13) as the factor of interest will be conducted on the natural logarithm (log) of the IgG concentrations.

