2, 5 μ g or PCV13) as the factor of interest will be conducted on the natural logarithm (log) of pneumococcal OPA titers and the natural log of the IgG concentrations.

In addition, for both Stage 1 Group 1 and Stage 2 Group 2, SP1500+0785 levels (ng/mL) will be collected for those subjects given either ASP3772 or PCV13. Levels of the following cytokines will be collected for subjects given ASP3772 or PCV13: Th17, IL-17, IL-17, IL-22, The units for all are pg/mL. Non-parametric methods will be used for these analyses. A Kruskal-Wallis test will be used to test for overall differences between the 3 dose levels and PCV13. All treatment groups in Stage 1 will be compared, followed by paired comparisons between each of the ASP3772 dose levels and PCV13 using a Wilcoxon Test. The same set of comparisons will be made for subjects in Stage 2, Group 2.

Stage 2; Group 3:

For the 11 serotypes contained in PPSV23 and not in PCV13, immunological response will be evaluated by the following endpoints at 30 days after administration of PPSV23:

- The GMFR, GSD and 95% CI in anticapsular polysaccharide IgG and OPA titer
- The proportion of subjects with a ≥ 4-fold increase in anticapsular polysaccharide IgG and OPA relative to baseline
- The GMT, GSD and 95% CI for the OPA titers
- The GMC, GSD and 95% CI for serotype-specific IgG levels.

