6.1.2 Secondary Endpoint(s)

Stage 1, Group 1:

Surrogate markers used to assess the immunological response on day 30 for the 13 serotypes common to ASP3772 and PCV13 are:

- Functional OPA activity for each serotype characterized by an OPA titer⁻¹ response expressed as the reciprocal of the serum dilution that causes a 50% reduction in the colony-forming units
- Pneumococcal serotype-specific anticapsular polysaccharide PS IgG for each serotype.

Summaries of immune response 30 days after immunization in adults 18 to 64 years of age will be provided for each serotype by treatment group (ASP3772 (1 µg, 2 µg, 5 µg) or PCV13) and stage. All adult subjects treated with PCV13 will be combined into a single group. To assess similarity between the 3 cohorts of PCV13 subjects, summaries will be provided by cohort for the PS IgG levels and the OPA titers.

Endpoints used to assess the immunological response on day 30 for the 11 serotypes unique to ASP3772 (2, 8, 9N, 10A, 11A, 12F, 15B, 17F, 20B, 22F, 33F) are:

- Geometric mean fold rise (GMFR) in anticapsular PS IgG at 30 days relative to pre-immunization
- Proportion of subjects with a ≥ 4 -fold increase in anticapsular PS IgG
- Functional OPA activity for each serotype characterized by an OPA titer⁻¹ response

Stage 2; Group 2:

Endpoints used to assess the immunological response on day 30 are:

- Functional OPA activity for each serotype characterized by an OPA titer⁻¹ response
- Pneumococcal serotype-specific anticapsular PS IgG for each serotype for the 13 serotypes contained in PCV13
- For each of the 11 serotypes unique to ASP3772, the GMFR in anticapsular PS IgG at 30 days relative to pre-immunization
- For each of the 11 serotypes unique to ASP3772, the proportion of subjects with a ≥ 4 -fold increase relative to baseline in anticapsular PS IgG for ASP3772 and PCV13-treated subjects

For Stage 2, Group 2 summaries will be provided by treatment group (ASP3772 (1 μ g, 2 μ g, 5 μ g) or PCV13) for all subjects age 65-85, for subjects 65-74 and for those 75-85. Subjects treated with PCV13 in cohorts 4, 5 and 6 will be combined into a single dose group and summarized by age (65-85, 65-74 and 75-85). To assess similarity between the 3 cohorts of PCV13 subjects, summaries will be provided by cohort for the PS IgG levels and the OPA titers.

In addition, for ASP3772, the following endpoints will be assessed.

- Dose response in the OPA titer⁻¹ for ASP3772
- Dose response in the PS IgG antibodies for ASP3772

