7.4 Analysis of Immunogenicity

7.4.1 Analysis of Immunogenicity Endpoints

Assessment of immunological response following ASP3772 administration relative to PCV13 is a secondary objective for this study.

Stage 1, Group 1 and Stage 2, Group 2:

The objective in Stage 1, Group 1 and Stage 2, Group 2 is to determine if ASP3772 stimulates an immunogenic response to the 13 pneumococcal serotypes that are also contained in PCV13 and to determine if ASP3772 stimulates an immunogenic response to an additional 11 serotypes contained in ASP3772. The following summaries will be given by treatment group (ASP3772: 1, 2, 5 μ g vs. PCV13) and stage for all serotypes.

OPA Titer

- GMT, GSD and 95% CI
- The ratio of the OPA GMT (each ASP3772 dose level/PCV13), the GSD and 95% CI for the ratio
- The GMFR relative to baseline, GSD and 95% CI
- The proportion of subjects with a $>$ 4-fold increase in OPA titer¹

IgG Concentration

- The GMC, GSD and 95% CI
- The ratio of the IgG GMC (each ASP3772 dose level/PCV13), the GSD and 95% CI
- The GMFR relative to baseline, GSD and 95% CI
- The proportion of subjects with a \geq 4-fold increase in anticapsular PS IgG

Values below the LLOQ will be set to $\frac{1}{2}$ LLOQ for calculation of geometric means and set to LLOQ for calculation of fold changes.

Summaries for Stage 2 subjects will be given for 65-85, 65-74 and 75-85-year olds.

An analysis of covariance (ANCOVA) model with age (65 to 74 years, 75 to 85 years) as the covariate and treatment (ASP3772 1, 2, 5 μ g) as the factor of interest will be conducted on the natural logarithm (log) of pneumococcal OPA titers and on the natural log of the IgG concentrations for each serotype to examine dose response. Provided the treatment effect is

significant, paired comparisons between the 5 μ g vs 1 μ g, followed by 5 μ g vs 2 μ g, followed by 2 μ g vs 1 μ g will be conducted. There are no adjustments to control for the Family-Wise Error Rate (FWER) for 3 comparisons for each of the 24 serotypes. A Cochran-Armitage trend test will be used to test for trend.

CCI

Stage 2; Group 3:

The objective for Stage 2, Group 3 is to obtain estimates of the immune response following PPSV23 for the 11 serotypes contained in PPSV23 and not in PCV13. Immunological response 30 days after administration of PPSV23 will be summarized as follows:

- The GMT, GSD and 95% CI for the OPA titers
- The GMC, GSD and 95% CI for serotype-specific IgG levels.

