- The GMFR, GSD and 95% CI in anticapsular polysaccharide IgG and OPA titer
- The number and percentage of subjects with a \geq 4-fold increase in anticapsular PS IgG and OPA relative to baseline.

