Proportion of subjects with a > 4-fold increase in OPA titer

SAS PROC FREQ can be used to obtain the proportions and 95 % CI for each serotype.
PROC FREQ data=xxxx order=freq;

```
tables fourfold / binomial (wilson) alpha=0.05;  
weight count;
```

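### The SAP counts OPA responders in Groups 1 and 2 at more than 4-fold, against at least 4-fold in the protocol and in its own Group 3 rule

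*SAP*

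**What the plan says.** The SAP states the OPA responder rule in three places, and they disagree.

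- SAP 7.4.1, Stage 1 Group 1 and Stage 2 Group 2: the last OPA bullet puts a strict greater-than sign before "4-fold increase in OPA titer". The matching IgG bullet in the next list uses ≥.
- SAP 10.1, Appendix A: the heading above the SAS code for the proportion reads "Proportion of subjects with a > 4-fold increase in OPA titer". It names no group.
- SAP 7.4.1, Stage 2 Group 3: a ≥ sign stands before "4-fold increase in anticapsular PS IgG and OPA relative to baseline", so both assays use at least 4-fold.

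The protocol uses at least 4-fold throughout. Its synopsis says for Stage 1: "The proportion of subjects with a ≥ 4-fold increase in anticapsular PS IgG and OPA relative to baseline will be calculated". The same rule appears for Stage 2 Group 2 in the synopsis and for both groups in Section 7.4. For Group 3, Section 7.4 has "The proportion of subjects with a ≥ 4-fold increase in anticapsular polysaccharide IgG", with OPA in the same bullet.

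On the scale of measurement, SAP 6.1.2 defines the OPA titer as the "reciprocal of the serum dilution that causes a 50% reduction" in colony-forming units. SAP 7.4.1 has values below the LLOQ "set to LLOQ for calculation of fold changes". Neither place says whether titers are interpolated between dilutions or reported at dilution steps.

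**The concern.** The SAP describes itself as a more detailed elaboration of the protocol's analysis, so an unannounced stricter threshold is a departure from the protocol as well as an internal conflict. Two programmers could each cite the SAP and produce different OPA responder tables.

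Two readings of the results are exposed. A Stage 2 secondary objective evaluates ASP3772 relative to PPSV23 for the serotypes outside PCV13. Under SAP 7.4.1, ASP3772 recipients in Group 2 would need more than a 4-fold OPA rise, while PPSV23 recipients in Group 3 would need only 4-fold. Within Groups 1 and 2, OPA and IgG responder rates for the same subjects would rest on different rules. If OPA titers come in two-fold steps, a rise of exactly 4 is a common result, and those subjects change category.

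**Working it through.** **1. The rules side by side**

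| Source | Groups 1 and 2, OPA | Groups 1 and 2, IgG | Group 3, OPA and IgG |
|---|---|---|---|
| Protocol synopsis and 7.4 | ≥ 4 | ≥ 4 | ≥ 4 |
| SAP 7.4.1 | > 4 | ≥ 4 | ≥ 4 |
| SAP Appendix A heading | > 4 (no group named) | not covered | > 4 for OPA, if read as applying to all groups |

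The visible entries in SAP Section 8 mention no change to the OPA threshold; three entries are redacted.

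**2. Direction**

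P(≥ 4-fold) − P(> 4-fold) = P(fold rise = 4), which cannot be negative. The strict rule therefore gives a rate lower than or equal to the protocol's.

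**3. Size**

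The plan states no OPA responder rate and no power figure based on this threshold, so there is nothing to reproduce. The documents also give no distribution of OPA fold rises. What follows is a sensitivity range under assumptions: log2 fold rise normal with mean μ and SD σ, and n = 99 per Stage 2 dose level or PPSV23 group (SAP 3.2).

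*Case A: titers on a two-fold grid.* Rounding the log2 rise to a whole number gives

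P(≥ 4) = 1 − Φ((1.5 − μ)/σ) and P(> 4) = 1 − Φ((2.5 − μ)/σ).

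- μ = 2, σ = 1.5: 1 − Φ(−0.333) = 0.631 against 1 − Φ(0.333) = 0.369. The gap is 26 points, about 26 of 99 subjects.
- μ = 3, σ = 2: 1 − Φ(−0.75) = 0.773 against 1 − Φ(−0.25) = 0.599. The gap is 17 points, about 17 of 99. The Wilson 95% intervals (the method in Appendix A) are 68.2% to 84.5% and 50.0% to 69.0%.

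Over μ = 1, 2, 3, 4, 5 and σ = 1, 1.5, 2, 2.5, 3:

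| μ | Gap in points, smallest to largest over σ |
|---|---|
| 1 | 12.5 to 24.2 |
| 2 | 13.2 to 38.3 |
| 3 | 12.5 to 24.2 |
| 4 | 6.1 to 12.1 |
| 5 | 0.6 to 8.1 |

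Placing the pre- and post-immunization titers on the grid separately (2,000,000 simulated subjects, σ = 2) gives gaps of 19.5, 17.4 and 12.1 points at μ = 2, 3 and 4. The formula gives 19.7, 17.5 and 12.1.

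*Case B: interpolated titers.* Here titers are rounded to whole numbers, the baseline log2 titer is normal with mean 6 and SD 2, and the rise has μ = 2 to 4 and σ = 2. The assumed LLOQ is 4, 8 or 16, with values below it set to it as the SAP directs. The simulated gap runs from 0.12 to 0.26 points. With fully continuous titers it is zero.

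**4. Which comparisons are touched**

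- Group 2 against Group 3: under SAP 7.4.1 the two groups use different rules. With the same true response in both (Case A, μ = 3, σ = 2), Group 2 would show 59.9% and Group 3 77.3%.
- OPA against IgG within Groups 1 and 2: different rules.
- ASP3772 against PCV13 within Groups 1 and 2: the same rule in both arms.

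**The case against.** **The sign may be an artefact of PDF reading.** An underlined greater-than sign can lose its stroke, and the 7.4.1 bullet has lost another: its titer exponent reads 1 where SAP 6.1.2 has −1. This doubt stands in part. Against it, the strict sign appears for OPA in two separate places, while ≥ survives for IgG in the same section and for OPA in Group 3.

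**A reader might infer that OPA responder rates are understated by a material amount.** The documents do not support that. It needs a sizeable share of rises of exactly 4, hence titers on a discrete grid, and no section says they are. A titer defined by 50% reduction fits interpolation at least as well. Only lower or equal is certain.

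**A reader might also infer that responder rates are not comparable in general.** That goes too far. The randomized comparison with PCV13 is like for like. Group 3 is nonrandomized and summarized separately, and no visible SAP text specifies a test or ratio of OPA responder rates against PPSV23. What is at risk is a descriptive side-by-side reading. If the Appendix A heading governs all groups, even the difference between Groups 2 and 3 disappears, but the SAP then contradicts its own Group 3 rule and the protocol.

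**The output is secondary.** The endpoint lists in Protocol 2.3 and SAP 6.1.2 name the 4-fold proportion for IgG only ("For each of the 11 serotypes unique to ASP3772, the proportion of subjects with a" at least 4-fold IgG rise, for Group 2). This is correct and limits the weight of the point. The OPA proportion is still a planned analysis in both documents.

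**Conclusion.** The point holds as a conflict of definitions. For OPA responders, SAP 7.4.1 (Groups 1 and 2) and the group-neutral Appendix A heading use more than 4-fold. The protocol uses at least 4-fold in every group, as does the SAP for Group 3.

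The direction is certain: lower or equal. The size cannot be fixed from the documents. It is about 0 to 0.3 points with interpolated titers. On an assumed two-fold grid it is 0.6 to 38 points over the inputs tried, and above 10 points at every setting with a mean log2 rise of 1 to 3. These figures rest on assumed normal log2 rises and assumed LLOQ values.

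The consequence is confined to OPA responder rates, read for Group 2 beside Group 3 or beside the IgG rates. Safety endpoints, sample size and power are untouched. All of this presumes that the source PDF carries the strict sign; if it shows ≥ in both places, the point falls away.

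**What to change.** Check the two signs in the source PDF. If they are strict, write at least 4-fold for OPA in SAP 7.4.1 (Stage 1 Group 1 and Stage 2 Group 2) and in the Appendix A heading, so that one protocol-consistent rule applies to all groups and both assays. Code the four-fold indicator in Appendix A to match.

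It would also help to add one sentence saying whether OPA titers are interpolated or reported at dilution steps, since that decides whether ties at exactly 4 matter.

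The cost is two symbols and, if wanted, one sentence. Any OPA responder table already programmed with the strict sign would need a rerun.
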